9.1 Observation of adverse events

- 1) Clinical adverse reactions: All subjects should be observed carefully for any adverse events that occur during the clinical study. The clinical manifestations, severity, occurrence time, duration, treatment methods and prognosis of adverse events should be recorded in time, and the correlation between adverse events and the investigational product should be determined.
- 2) Abnormal laboratory tests results: Subjects with abnormal results of the above tests after medication should be closely followed up and observed until they return to normal or stable, and the correlation between abnormality and the investigational product should be determined.

9.2 Criteria for determining adverse event (AE) severity

- 1) Mild: Complain of discomfort, and not requiring symptomatic treatment or drug discontinuance;
- 2) Moderate: Complain of discomfort, requiring symptomatic treatment, not requiring drug discontinuance but requiring reduction of the drug dose by 25%;
- 3) Severe: Complain of significant discomfort, requiring symptomatic treatment and drug discontinuance.

9.3 Criteria for determining the relationship between adverse event (AE) and the investigational product

According to the criteria for determining the causality between the drug and AEs, the correlation between AEs and the investigational product is divided into five grades: definitely related, probably related, possibly related, possibly unrelated, and definitely unrelated. The three conditions of definitely related, probably related, and possibly related are classified as adverse reactions caused by the investigational product. The total number of subjects with investigational product-related adverse reactions is taken as the numerator, and the number of all enrolled subjects for adverse reaction evaluation is taken as the denominator to calculate the incidence rate of adverse reaction. Please refer to Table 2 for specific determination.

Clinical Study Protocol

Version No.: V2.0

Table 2. Criteria for determining the causality of adverse drug reactions

Indicator	Definitely related	Probably related	Possibly related	Possibly unrelated	Definitely unrelated
Reasonable chronological sequence	Yes	Yes	Yes	Yes	No
Conforming to the known reaction type of the investigational product	Yes	Yes	Yes	No	No
Improving after the discontinuance of the investigational product	Yes	Yes	Yes or No	Yes or No	No
Recurring after reusing the investigational product	Yes	?	?	?	No
Possible other explanation for the drug-induced reaction	No	No	Yes	Yes	Yes

Note: ? means that the medicine is not allowed to be administrated again due to medical ethics. "Possibly unrelated" indicates that further observation is needed for evaluation.

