Discontinuation criteria:	
Trial discontinuation means the clinical trial is not completed according to protocol and is prematurely discontinued. The main purpose of trial discontinuation is to protect the rights and interests of the subjects, ensure the quality of the trial, and avoid unnecessary economic losses.
 
(1) If serious safety issues occur during the trial, the trial should be discontinued in time;
 
(2) During the trial, major errors are found in the clinical trial protocol that make evaluation of drug efficacy difficult; or major deviations from the well-designed protocol are found in the implementation that make evaluation of drug efficacy difficult if the trial is to be continued;
 
(3) The sponsor requests to discontinue the trial (because of economic or management factors or others);
 
(4) The administrative department in charge rescinds the trial.

Dose design and treatment regimen:	
Patients will receive local rectal short-course radiotherapy. Radiotherapy will employ conformal or intensity-modulated radiation therapy, with a pelvic irradiation dose of 25 Gy/5 Fractions/1 week. Then rest for 1 week after radiotherapy and begin to receive neoadjuvant chemotherapy CAPOX and PD1 inhibitor for immunotherapy, for 2 cycles. One week after the completion of neoadjuvant therapy, a second evaluation on the primary lesions will be performed, and the surgical method is total mesorectal excision. Postoperative adjuvant therapy will be started 3-4 weeks after surgery, and the treatment regimen will be determined by the investigator. The efficacy of neoadjuvant therapy on postoperative specimens will be evaluated in accordance with Rectal Cancer Regression Grade. Treatment-related toxic and side effects will be evaluated as per CTCAE 5.0 toxic and side effects evaluation criteria.

Statistical method:	
This study will employ SPSS 16.0 statistical software package for analysis. EFS and OS will be analyzed using the Kaplan-Meier method and log-rank test.

Trial schedule:	
Estimated start time of the trial: Oct. 2019
 
Estimated time of enrollment completion: Oct. 2021
 
Estimated end time of the trial: Dec. 2025

Version No.:	V2.0

Clinical Study Protocol

Version No.: V2.0

List of Abbreviations

Abbreviations and statistics descriptions (English)

dMMR	Deficient mismatch repair protein
MSI	Microsatellite instability
mCRC	Metastatic Colorectal Cancer
PD-1	Programmed cell death protein 1

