5.3 Technical routes

5.4 Precautions

(1) Palpitation, chest tightness, dyspnea, cold limbs, and lowered blood pressure during chemotherapy should be observed closely, which indicate that the patient may have allergic reaction. Therefore, the treatment should be stopped immediately and the condition should be actively treated as allergic reaction.

(2) The dose-limiting toxicity of oxaliplatin is neurotoxicity, mainly in peripheral sensory nerves, manifested as sensory disturbance or/and paresthesia in the extremities. With or without algospasm, which is often cold-induced. These symptoms occur in 85-95% of patients receiving treatment. The symptoms usually decrease in treatment intervals, but gradually worsen with the increase of treatment cycles. Dysfunction includes an inability to perform fine movements, which is related to sensory disturbance. Evaluation with Levi sensory neurotoxicity classification criteria: 1) grade 0: no; 2) grade 1: paresthesia or dysesthesia (cold-induced), can be resolved within 1 week; 3) grade 2: paresthesia or dysesthesia, can be completely resolved within 21 days; 4) grade 3: paresthesia or dysesthesia, cannot be completely resolved within 21 days; 5) grade 4: paresthesia or dysesthesia, accompanied with dysfunction. The duration of the patient's symptoms and severity of pain and/or dysfunction are the indications for dose adjustment, and sometimes even treatment discontinuation is needed. When the treatment is discontinued, the neurological symptoms usually may improve.

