8.2 Efficacy evaluation

Study endpoints

The primary endpoint was pathological complete response (pCR) rate, pCR was defined as the absence of viable tumour cells in the resected primary tumour specimen and all sampled regional lymph nodes (ypT0N0).

Secondary endpoints were 3-year event-free survival rate (defined as the percentage of patients without disease recurrence or progression or death due to any cause after 3-year follow-up), R0 resection rate (defined as the rate of negative margin microscopically), 3-year OS rate (defined as the percentage of patients alive after 3-year follow-up), complication rate, safety, and quality of life. Adverse events (AEs), duration of which collection was from the time the patient signed the informed consent form to 90 days after surgery, were graded according to the National Cancer Institute Common Terminology Criteria for Adverse Events, version 5.0.

Biomarker analysis

Tissue samples or paraffin sections must be provided as a patient was enrolled. Immunohistochemistry was performed to detect the expression of PD-L1 and DNA mis-match repair (MMR) proteins (MSH6, MSH2, MLH1 and PMS2). PD-L1 combined positive score (CPS) was evaluated using PD-L1 IHC 22C3 pharmDx (Agilent Technologies Inc., California, USA), defined as the number of PD-L1 positive cells (tumour cells, lymphocytes, macrophages) as a proportion of the total number of tumour cells multiplied by 100, Positive PD-L1 expression was considered when CPS was 1 or more. Comprehensive genomic profiling was conducted using targeted gene capture-based next-generation sequencing technology. Briefly, for formalin-fixed paraffin-embedded (FFPE) tissues, hematoxylin and eosin staining (H&E staining) was performed, and the stained sections were evaluated by a pathologist to ensure the tumor cells of $\geq 20\%$. DNA was extracted from the tumor tissues of patients using standard methods. A panel of 418 genes was captured and then sequenced through the Illumina NovaSeq6000 platform (Illumina, San Diego, USA) with 2×150 bp paired-end reads. The average of sequencing depth of tumor

tissues was $\geq 1000X$. Genomic alterations including tumor mutation burden (TMB), single nucleotide variants (SNV), short and long insertions and deletions (INDELs), copy number variants (CNV), and gene fusions were assessed.

Statistical analysis

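### Section 9.2 grades adverse event severity on a treatment-and-drug-action scale that contradicts the CTCAE 5.0 grading required elsewhere and has no level for a treated event with no dose change

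*Protocol*

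**What the plan says.** Two places in the protocol name CTCAE 5.0. In the synopsis, the row on dose design and treatment regimen states: "Treatment-related toxic and side effects will be evaluated as per CTCAE 5.0". Section 8.2 says that AEs, collected from consent to 90 days after surgery, "were graded according to the National Cancer Institute Common Terminology Criteria for Adverse Events, version 5.0".

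Section 9.2 carries the heading for determining AE severity and does not mention CTCAE. Its three levels are:

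- "Mild: Complain of discomfort, and not requiring symptomatic treatment or drug discontinuance"
- "Moderate: Complain of discomfort, requiring symptomatic treatment, not requiring drug discontinuance but requiring reduction of the drug dose by 25" percent
- "Severe: Complain of significant discomfort, requiring symptomatic treatment and drug discontinuance"

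Sections 7.3 and 9.1 tell investigators to record the severity of clinical adverse events but name no scale. Section 5.4 has a separate 0 to 4 scale, for oxaliplatin sensory neurotoxicity only.

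**The concern.** Two instructions cover the same attribute of the same events in the same patients. An investigator who follows 8.2 assigns a CTCAE grade. One who turns to the section headed as the severity criteria assigns mild, moderate or severe by a different rule. The protocol does not map one scale to the other or limit either to a purpose.

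Safety is a listed secondary endpoint and the whole of the secondary objective in section 2. Severity is assigned at the site and entered on the case report form. A statistical analysis plan written later can choose how to tabulate grades, but it cannot restore a CTCAE grade that was never recorded because the site used 9.2. The matter therefore belongs in the protocol.

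**Working it through.** No figure in the plan is at issue, so the check is a comparison of texts followed by a test of whether 9.2 covers the events it must classify.

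**Step 1: do the two scales overlap?**

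| Source | Events covered | Basis of severity |
|---|---|---|
| Synopsis | Treatment-related toxicity | CTCAE 5.0 |
| 8.2 | All AEs, consent to 90 days after surgery | CTCAE 5.0 |
| 9.2 | AEs, no restriction stated | Complaint, symptomatic treatment, drug action |
| 5.4 | Oxaliplatin sensory neurotoxicity | Own 0 to 4 scale |

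The rows for 8.2 and 9.2 cover the same events by different criteria. The 5.4 scale covers one toxicity and does not settle which of the two applies to the rest.

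**Step 2: is 9.2 complete on its own terms?** The levels use two main conditions: symptomatic treatment required (no or yes) and drug action required (none, 25% reduction, discontinuance). That gives 2 × 3 = 6 combinations.

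| Treatment required | Drug action required | Level under 9.2 |
|---|---|---|
| No | None | Mild |
| No | 25% reduction | Unclear: Mild does not rule it out, but only Moderate mentions reduction |
| No | Discontinuance | None |
| Yes | None | None |
| Yes | 25% reduction | Moderate |
| Yes | Discontinuance | Severe, if discomfort is significant |

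The fourth row carries the point. An event that calls for symptomatic treatment while the drugs continue at full dose is shut out of Mild by the treatment, out of Moderate by the missing 25% reduction, and out of Severe by the missing discontinuance. This follows directly from the wording. The second and third rows are also untidy, but the conclusion does not rest on them.

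**Step 3: what is the 25% a reduction of?** Section 9.2 does not name the drug. Section 5.2 gives oxaliplatin and capecitabine per square metre and camrelizumab only as a flat 200 mg, with no reduced dose. The reduction is thus a dosing rule placed inside a severity definition, without a stated target.

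**Step 4: which severity measure do the analyses use?** The safety comparison in 11.2 covers all AEs, severe adverse events and adverse reactions. Section 9.4 defines the second of these by outcomes: death or threat to life, disability, partial loss of living ability, and longer hospital stay. Those are seriousness criteria, and the abbreviation list expands SAE with the word serious. So 11.2 does not use the 9.2 levels, but its wording coincides with the name of the top level in 9.2.

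**The case against.** The strongest reply is that CTCAE plainly governs what is reported. Section 8.2 defines the endpoint and assigns CTCAE 5.0 to all AEs in the collection window, the synopsis agrees for treatment-related toxicity, and no analysis calls on the 9.2 levels. On this view 9.2 is leftover text. Most of this stands, and it limits the harm to recording. It does not remove the contradiction, because the protocol nowhere sets 9.2 aside and that is the section an investigator would consult for severity.

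A reader might infer more than the text supports in four ways:

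- **Laboratory abnormalities.** Each 9.2 level starts from a complaint, so a symptom-free laboratory change seems to have no level. But in 7.3 and 9.1 the instruction to record severity sits under clinical events. The laboratory item asks for follow-up and causality, and 11.2 describes laboratory results as normal or abnormal. Nothing clearly sends them to 9.2.
- **Neurotoxicity.** Section 5.4 says the duration of symptoms and "severity of pain and/or dysfunction are the indications for dose adjustment, and sometimes even treatment discontinuation is needed". One might argue that an event at "grade 3: paresthesia or dysesthesia, cannot be completely resolved within 21 days", handled by dose reduction alone, becomes Mild. That reads 9.2 by the action taken, whereas 9.2 speaks of what the event requires. It also ignores that reduction is named under Moderate. This toxicity has its own scale in any case.
- **Events after surgery.** A scale built on drug action suits these poorly, but surgical complications are a separately listed endpoint, and adjuvant drugs may still need to be changed.
- **Size.** Section 5.4 says of oxaliplatin neurotoxicity: "These symptoms occur in 85-95% of patients receiving treatment". Applied to 30 patients this gives 0.85 × 30 = 25.5 to 0.95 × 30 = 28.5. That counts patients with neurotoxicity and says nothing about how many events would be graded differently.

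**Conclusion.** The point holds in a limited form. Section 9.2 is a second severity scale for the same events, it contradicts CTCAE 5.0, and it cannot classify a clinical event that is treated without a dose change. This is a stated rule that fails, not a detail left for later, and it should be corrected.

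The consequence is confined to how severity is recorded for a secondary endpoint. The share of events graded differently, or left ungraded under 9.2, cannot be computed from the protocol. It would be wrong to conclude that the reported safety endpoint has no defined grading, since 8.2 supplies one. It would also be wrong to conclude that the severe adverse event rate in 11.2 is built on the top level of 9.2, since 9.4 defines it by outcomes; that is a terminology error only.

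The conclusion assumes that 9.2 is meant to be applied as its heading says. If it is leftover text, the same correction is still the right one.

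**What to change.** Replace the three levels in 9.2 with: *AE severity is graded 1 to 5 by NCI CTCAE version 5.0; symptomatic treatment and action taken with each drug are recorded separately and do not determine the grade.*

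Do not simply delete the levels. Section 9.2 is the only place that quantifies a dose reduction, so the 25% should move to a separate dose-modification rule that names the drugs it applies to and says what is done with camrelizumab. Keep the neurotoxicity scale in 5.4 for adjusting oxaliplatin.

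As a secondary correction, write serious adverse events in 9.4 and 11.2.

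The cost is mainly wording. No new assessments are needed, because 8.2 already requires CTCAE 5.0 grading. The one decision of substance is which drugs the 25% reduction covers. If the case report form, which is not shown, has a mild/moderate/severe field, that field would change to a CTCAE grade.

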9.4 Severe adverse event handling and reporting methods

The severe adverse events (that is, death or life threatening, disability, or loss of partial living ability, and prolongation of length of stay) occurred during the trial, whether or not related to the trial and the investigational product, should be treated promptly and actively based on symptoms to minimize the loss of patients, be immediately reported to the principal investigator, and be notified to the trial sponsor within 24 hours.

10. Data management

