5.2 Administration method

CAPOX: Oxaliplatin 130 mg/m² iv d1
Capecitabine 1000 mg/m² po bid, d1-14, q3w;

PD1 inhibitor camrelizumab: 200 mg iv drip, q3w;

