11.2 Statistical analysis plan

Statistical analysis should employ the two-sided test, and $P \leq 0.05$ indicates a statistically significant difference (unless otherwise specified).

The Continuous data should be statistically described by mean, median, standard deviation, maximum value, and minimum value; the categorical data or ranked data should be statistically described by frequency.

The test should be used to compare the Continuous data between the groups, and the χ^2 test or rank sum test should be used to compare the categorical data between the groups.

Efficacy evaluation method: the evaluation of primary efficacy evaluation indicator: the overall response rate between the experimental group and the control group should be compared by the superiority test. Hypothesis test is

$$H_0: \pi_T = \pi_C, H_1: \pi_T > \pi_C$$

The 95% CI of the difference in overall response rate between the experimental group and the control group should be calculated, and the lower limit > 0 can be considered as the establishment of superiority. Meanwhile, CMH- χ^2 with central effect should be used for comparison between groups.

Safety evaluation methods: the χ^2 test/Fisher's precision probability test should be used to compare the incidence rates of all adverse events, severe adverse events and adverse reactions between the two groups, and the normal/abnormal changes in laboratory test results before and after treatment should be described.

SAS 9.2 software should be employed for statistical analysis, and the analysis process should be all programmed.

12. Quality control of the clinical trial

(1) The preparation of test vesicle packaged chemotherapeutic drugs provided by the sponsor should conform to the relevant regulations and conditions and be subject to strict quality control.

(2) In the process of clinical study, the clinical research associate assigned by the sponsor should visit the study hospital regularly and faithfully make the inspection records to ensure that the study protocol is strictly followed and all CRFs can be filled in accurately.

(3) The laboratory tests should be conducted by study sites in accordance with the standard operating procedures (SOP). The testing methods and quality control of different study sites should be unified.

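### The expedited-reporting list in 9.4 covers a prolonged hospital stay but not a new or repeat admission, so an unplanned admission that meets no other criterion gets no 24-hour notice

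*Protocol*

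**What the plan says.** Section 9.4 of the protocol defines the reportable category in a parenthesis that opens with 'that is': death or threat to life, "disability, or loss of partial living ability, and prolongation of length of stay". Events in it must "be immediately reported to the principal investigator, and be notified to the trial sponsor within 24 hours", and this applies "whether or not related to the trial and the investigational product".

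Section 9.2 uses the word 'severe' differently, as the top step of a three-step intensity scale: "Severe: Complain of significant discomfort, requiring symptomatic treatment and drug discontinuance". That scale does not mention hospitalisation and has no reporting deadline attached.

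For adverse events in general, section 9.1 says "All subjects should be observed carefully for any adverse events that occur during the clinical study", with timely recording but no 24-hour notice. Section 11.2 names the category as an analysed safety outcome: the plan is to "compare the incidence rates of all adverse events, severe adverse events and adverse reactions between the two groups".

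**The concern.** The 9.4 list treats added time in hospital as a mark of seriousness, but only for a patient who is already an inpatient. The same event is expedited if it lengthens a stay. If it brings the patient in from outside, it is not expedited unless it is also fatal, life threatening or disabling. Because reporting does not depend on causality, the list alone decides what is expedited, and a gap in it is not made good by the investigator's causality assessment.

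The design leaves room for such admissions. Capecitabine is an oral drug given "po bid, d1-14, q3w" (5.2). Section 5.4 foresees immune-related events in several organs and asks for subjects to be taught to monitor themselves. Under 8.2, adverse events are collected until 90 days after surgery, so a readmission after surgical discharge can fall inside the collection window and outside the list.

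Two things are at stake: prompt notice of these admissions to the principal investigator and the sponsor and, depending on how 11.2 is read, their inclusion in a reported safety rate. Safety is the secondary objective and a secondary endpoint of the trial.

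**Working it through.** The plan gives no figure to reproduce. The check is mainly one of wording.

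**Step 1. Is the 9.4 list closed?** Yes. It is introduced by 'that is', not by 'such as' or 'including', and it has no catch-all for other medically important events.

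**Step 2. Does another section supply the missing criterion?**

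| Place in the protocol | What it provides | Adds new admission? |
|---|---|---|
| List of Abbreviations | Expands SAE, using 'serious'; no definition | No |
| 7.3 and 9.1 | Timely recording of all adverse events with severity, timing, treatment and causality | No |
| 8.2 | CTCAE 5.0 grading; collection from consent to 90 days after surgery | No |
| 9.2 | Intensity scale based on discomfort, treatment and drug discontinuance | No |
| 11.1 | Definition of the safety set | No |
| 11.2 | Incidence of 'severe adverse events', not defined there | No |

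**Step 3. Apply the rule to cases.**

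| Event | Expedited under 9.4? | Recorded as an adverse event? |
|---|---|---|
| Fatal, life threatening, disabling or causing partial loss of living ability, with or without admission | Yes | Yes |
| Arises in hospital and lengthens the stay | Yes | Yes |
| Causes an unplanned admission, then a complication lengthens that stay | Yes, once the stay is prolonged | Yes |
| Causes an unplanned admission and meets no other criterion | **No** | Yes |

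Only the last row is affected.

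**Step 4. Size of the effect on a reported rate.** This matters only if 11.2 means the 9.4 list. A patient-level rate is (patients with at least one qualifying event) / N. A patient adds to the shortfall only if the admission is that patient's sole potentially qualifying event. A second such admission in the same patient, or an admission in a patient already counted, changes nothing.

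- With k such patients, the shortfall is k/N.
- With N = 30 (planned enrolment; 8.2 bases safety analyses on all enrolled patients) and k = 1: 1/30 = 0.033, or 3.3 percentage points.
- The safety set in 11.1 requires at least one treatment and actual safety data, so N could be below 30 and the contribution per patient slightly larger. Its size is not stated. Purely as an illustration, if N were as low as 24 (the sample size before the dropout allowance), it would be 1/24 = 0.042, or 4.2 points.
- k cannot be estimated: the protocol gives no admission rate and does not say whether cycles are given to inpatients or outpatients.

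**The case against.** The best defence is that little is lost. The gravest admissions are still expedited through the other criteria. The rest are recorded under 7.3 and 9.1 and graded by CTCAE 5.0 under 8.2. The primary endpoint, sample size and survival endpoints are untouched. Sections 6 and 16 bind the trial to Chinese GCP and to national law, whose reporting definitions may be wider. The wording may be a loss in translation. All of this stands as a limit on the consequence. It does not remove the gap. A general commitment to GCP does not say what a site should do when the protocol gives its own closed list, and the content of those rules cannot be seen in this document.

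A reader might infer more than the protocol supports in four ways:

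- *That all toxicity leading to hospital escapes 24-hour reporting.* It does not; see the first and third rows of the case table.
- *That much of the important toxicity would first appear as a new admission.* Oral dosing and the possibility of onset between infusions make this plausible, but no passage gives a frequency.
- *That these admissions would be missing from the evidence for stopping the trial over serious safety issues under 4.5.* That criterion is not tied to the 9.4 list, and the events remain in the adverse event data. What is lost is the prompt notice and the label.
- *That 11.2 certainly under-counts.* The term there could mean the 9.4 list or the 9.2 grade. The sentence is also written for a two-group comparison, although section 3 describes a single-arm trial. The link to the rate is therefore conditional.

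Conversely, one might read the 9.2 'severe' grade into 9.4 and so widen the reporting duty. The closed parenthesis in 9.4 does not support that reading.

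**Conclusion.** The point holds in a limited form. Section 9.4 states a rule that makes a prolonged stay reportable within 24 hours and leaves out a new or repeat admission, and nothing else in the protocol corrects it. This is a definition fixed badly in the protocol itself, not a detail that could be left to a statistical analysis plan.

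The events affected are unplanned admissions that meet no other 9.4 criterion. They lose expedited notice; they are not lost to adverse event collection. The effect on a reported rate is at most 3.3 percentage points per patient with no other qualifying event. That figure assumes that 'severe adverse events' in 11.2 means the 9.4 list and that all 30 patients are in the denominator. The total effect cannot be computed from the protocol. The change should be made because the gap concerns safety reporting and is simple to close; the efficacy conclusions do not depend on it.

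**What to change.** In 9.4, replace the prolonged-stay item with: *hospital admission or prolongation of an existing stay, excluding planned admissions for study treatment or surgery*. The exclusion is needed because every patient is scheduled for resection, and without it routine admissions would be reported.

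Use *serious* for this list in 9.4 and in 11.2, as the List of Abbreviations already does, and keep *severe* for the intensity grade in 9.2. This also settles which category 11.2 counts.

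The cost is one line of wording and a consistent change of term. In operation, expect a few more expedited reports and possibly a higher reported serious-event rate. Dosing, treatment and the efficacy analyses are not affected.
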